## **9.2.2.10.** Spirometry

Spirometry measurements include FVC (L), FEV1 (L), FEV1/FVC (%), PEF (L/s), FEF 25-75 (L/s). Spirometry (American Thoracic Society [ATS]/European Respiratory Society [ERS]-compliant) (Graham, 2019), as adjudicated by the site investigator, will be performed locally during the study at specified time points (Table 3). Spirometry details will be available in a separate operational manual provided to the sites.

Spirometry will be performed in-clinic at screening and randomization for all patients to exclude any patients with abnormal lung function and/or poorly controlled asthma. FEV1 eligibility criteria

are specified in exclusion criteria (Section 7.2.2). After randomization, spirometry will only be done in patients with co-morbid asthma.

Spirometry will be performed after a washout period of bronchodilators according to their action duration to avoid interference with spirometry assessments and the investigator will discuss this with the patients. Examples of washout periods that investigator can discuss with the patient include withholding the last dose of short acting bronchodilator (SABA, such as salbutamol/albuterol or levosalbutamol/levalbuterol) for at least 6 hours, long acting bronchodilator (LABA, such as formoterol or salmeterol) for at least 12 hours, ultra-long-acting LABA (such as vilanterol, indacaterol) for at least 24 hours, short acting muscarinic antagonist (SAMA, such as ipratropium) for at least 8 hours, and long acting muscarinic antagonist (LAMA, such as tiotropium, umeclidinium) for at least 24 hours. Withholding times will be verified before performing the measurements.

# 9.2.2.11. Evaluation of Cat Exposure

Patients will be asked about their exposure to cat(s) at study visits as outlined in Table 3. From week 48 through week 60, as part of the patient reported e-diary, patients will be asked to report exposure to their cat(s). At the screening, baseline, and randomization visits, exposure to cat(s) is assessed via the inclusion/exclusion criteria.

# 9.2.2.12. Patient Experience Assessment

Patients will complete questions at week 60 (Table 3) to assess various parameters that may impact efficacy assessments. Questions will assess changes that patients experienced over the course of the study regarding the amount of time spent with their cat(s) and the impact on their perceived health status.

# 9.2.3. Efficacy Procedures for Patients with Asthma

## 9.2.3.1. Asthma Nighttime Symptom Diary Score

Only for patients with asthma, upon waking up in the morning, patients will complete the e-dairy to report asthma symptoms experienced during the nighttime using the Asthma Nighttime Symptom Diary (ANSD). The ANSD score will be based on 6 patient-reported symptoms (difficulty breathing, wheezing, shortness of breath, chest tightness, chest pain, and cough at their worst using an 11-point numeric rating scale (NRS) ranging from 0 ('None') to 10 ('As bad as you can imagine').

## 9.2.3.2. Asthma Daytime Symptom Diary Score

Only for patients with asthma, before going to bed for the night, patients will complete the e-diary to report asthma symptoms experienced during the day using the Asthma Daytime Symptom Diary (ADSD). The ADSD score will be based on 6 patient-reported symptoms (difficulty breathing, wheezing, shortness of breath, chest tightness, chest pain, and cough at their worst using an 11-point numeric rating scale (NRS) ranging from 0 ('None') to 10 ('As bad as you can imagine').

# 9.2.3.3. Asthma Daily Symptom Score

Only for patients with asthma, average of daily scores of the ANSD score and the ADSD score will be used to generate an Asthma Daily Symptom Score (ADSS) ranging from 0 ('None') to 10 ('As bad as you can imagine').

#### 9.2.3.4. Nighttime Awakenings

Only for patients with asthma, patients will report the number of nighttime awakenings by completing the e-diary every morning.

#### 9.2.3.5. Rescue Medication Use

Only for patients with asthma, patients will report the number of rescue medication puffs (example-short-acting bronchodilator) by completing the e-diary every evening.

## 9.2.3.6. Juniper Asthma Control Questionnaire

Only for patients with asthma, the ACQ-5, (5-question version of the Juniper ACQ), is a validated questionnaire to evaluate asthma control. The ACQ-5 score is the mean of the scores of the 5 items and ranges from 0 (totally controlled) to 6 (severely uncontrolled). Scores less than 1.0 reflect adequately controlled asthma, and scores 1.0 or greater reflect inadequately controlled asthma. Higher score indicates lower asthma control and 0.5 is the smallest change that can be considered clinically important.

## 9.2.4. Safety Procedures for All Patients

## **9.2.4.1. Body Weight**

Body weight will be assessed using calibrated scales. Body weight will be recorded to the nearest 0.1 kg.

## **9.2.4.2.** Vital Signs

Vital signs, including temperature, sitting blood pressure, pulse, and respiration, will be collected predose.

# 9.2.4.3. Physical Examination

A thorough and complete physical examination will be performed. Care should be taken to examine and assess any abnormalities that may be present, as indicated by the patient's medical history.

## 9.2.4.4. Electrocardiogram

A standard 12-lead ECG will be performed. Heart rate will be recorded from the ventricular rate and the PR, QRS, and QT (identify QTcB or QTcF) intervals will be recorded. The ECG strips or reports will be retained with the source.

## 9.2.4.5. Laboratory Testing

Hematology, chemistry, urinalysis, and pregnancy testing samples will be analyzed. Detailed instructions for blood sample collection are in the laboratory manual provided to study sites.

Samples for laboratory testing will be collected. Tests will include:

## **Blood Chemistry**

Sodium Total protein, serum Aspartate aminotransferase (AST)
Potassium Creatinine Alanine aminotransferase (ALT)

Chloride Blood urea nitrogen (BUN) Alkaline phosphatase

Carbon dioxide Total bilirubin Albumin

Calcium Glucose

## **Hematology**

Hemoglobin Differential:
Hematocrit Neutrophils
Red blood cells (RBCs) Lymphocytes
White blood cells (WBCs) Monocytes
Red cell indices Basophils
Platelet count Eosinophils

#### **Urinalysis**

Color Glucose RBC
Clarity Blood WBC
pH Bilirubin Bacteria
Specific gravity Leukocyte esterase Epithelial cells

Ketones Nitrite Yeast

Protein

#### Other Laboratory Tests

Patients will be tested for FSH levels (if postmenopausal status is in question) and will undergo serum and urine pregnancy testing (women of childbearing potential only); pregnancy testing is not required of women confirmed to be menopausal. Samples will be collected for quantitative assessment of allergen specific IgE.

## Abnormal Laboratory Values and Laboratory Adverse Events

All laboratory values must be reviewed by the investigator or authorized designee.

Significantly abnormal test results that occur after start of treatment must be repeated to confirm the nature and degree of the abnormality. When necessary, appropriate ancillary investigations should be initiated. If the abnormality fails to resolve or cannot be explained by events or conditions unrelated to the study drug or its administration, the Medical/Study Director must be consulted.

The clinical significance of an abnormal test value, within the context of the disease under study, must be determined by the investigator.

Criteria for reporting laboratory values as an adverse event (AE) are provided in Section 10.1.1.

## 9.2.5. Drug Concentration and Measurements

Samples for drug concentration measurement will be collected at visits listed in Table 3.

#### 9.2.6. Immunogenicity Measurements and Samples

Samples for ADA assessment for REGN1908 and REGN1909 will be collected at time points listed in Table 3. Anti-REGN1908 and anti-REGN1909 neutralizing antibody (NAb) analysis may be performed on ADA positive serum samples. The overall immunogenicity risk will be taken into consideration to assess the need for NAb analysis. Serum samples will be banked if NAb analysis is to be conducted at a later time. Detailed instructions for blood sample collection are included in the laboratory manual provided.

## 9.2.7. Pharmacodynamic and Exploratory Biomarker Procedures

Blood samples will be obtained for additional exploratory research to better understand the effects of various anti-Fel d 1 antibodies on cat allergy. This will include the assessment of effective competition between REGN1908 and REGN1909 (either alone or in combination) and endogenous sIgE in serum for allergen binding in an in vitro interference/inhibition assay.

These results will be part of exploratory research analysis and will be included in an exploratory biomarker report, which will not be described in the clinical study report.

#### 9.2.8. Future Biomedical Research (Optional)

Patients who agree to participate in the future biomedical research (FBR) sub-study will be required to consent to this optional sub-study before samples are banked for FBR. Residual biomarker samples for study-related research, as well as unused PK and ADA samples, will be stored for up to 15 years after the final date of the database lock (or for a shorter time period if required per regional laws and regulations). The samples may be utilized for FBR that may or may not be directly related to the study, including being used as reference samples and assay development or validation. The results of these future biomedical research analyses will not be presented in the CSR.

# 9.2.9. Pharmacogenomic Analysis (Optional)

Patients who agree to participate in the genomics sub-study will be required to consent to this optional sub-study before collection of the samples. Whole blood samples for DNA extraction should be collected on day 1/baseline (predose), but can be collected at a later study visit. Whole blood samples for RNA extraction will be collected at time points according to Table 3. DNA and RNA samples will be collected for pharmacogenomics analyses to understand the genetic determinants of efficacy and safety associated with the treatments in this study and the molecular basis of cat allergy and related diseases. These samples will be single-coded as defined by the International Council for Harmonisation (ICH) guideline E15. Samples will be stored for up to 15 years after the final date of the database lock (or for a shorter time period if required per regional laws and regulations). If there are specific site or country requirements involving the pharmacogenomic analyses which the sponsor is unable to comply with, samples will not be collected at those sites.

The purpose of the pharmacogenomic analyses is to identify genomic associations with clinical or biomarker response to REGN1908-1909 treatment, cat allergy or related allergic diseases, clinical outcome measures, and possible AEs. In addition, associations between genomic variants and prognosis or progression of cat allergy as well as related allergic diseases may also be studied. These data may be used or combined with data collected from other studies to identify and validate genomic markers related to the study drug, target pathway, or cat allergy and related diseases.

Analyses may include sequence determination or single nucleotide polymorphism studies of candidate genes and surrounding genomic regions. Other methods, including whole-exome sequencing, whole-genome sequencing, DNA copy number variation, and transcriptome sequencing (or other methods for quantitating RNA expression) may also be performed. The list of methods may be expanded to include novel methodology that may be developed during the course of this study or sample storage period. Results from the genomic analyses will not be reported in the CSR.

## 10. SAFETY EVALUATION AND REPORTING

# **10.1.** Recording and Reporting Adverse Events

#### 10.1.1. General Guidelines

The investigator must promptly record all clinical events occurring during the study data collection, from the time of signing the ICF to the end of on-treatment period (see Section 11.4.6.1). Medical conditions that existed or were diagnosed prior to the signing of the Informed Consent will be recorded as part of medical history. Abnormal laboratory values and vital signs observed at the time of Informed Consent should also be recorded as medical history. Any subsequent worsening (ie, any clinically significant change in frequency and/or intensity) of a pre-existing condition that is temporally associated with the use of the study drug should also be recorded as an AE.

At each visit, the investigator will determine whether any AEs have occurred by evaluating the patient. Adverse events may be directly observed, reported spontaneously by the patient, or by questioning the patient at each study visit. Patients should be questioned in a general way, without asking about the occurrence of any specific symptoms. The Investigator must assess all AEs to determine seriousness, severity, and causality, in accordance with the definitions in Section 10.2. The Investigator's assessment must be clearly documented in the site's source documentation with the Investigator's signature. The Investigator should follow up on SAEs (and AESIs) until they have resolved or are considered clinically stable; AEs should be followed until they are resolved or last study visit, whichever comes first.

Although not considered an adverse event, if a pregnancy occurs during the study, information about the progress and outcome of the pregnancy will be collected. This should include the date that the subject became pregnant, information about the health of the subject, any medication treatments received during the pregnancy, any medical problems affecting or related to the pregnancy and/or the baby, whether the pregnancy came to term, the date of the child's birth, and the health of the child after birth. To collect this information, the study staff should contact the subject every trimester for updates on the pregnancy. The subject should also be asked to contact the site as soon as possible in the event of any medical problem affecting or related to the pregnancy and/or baby. Once the baby is born, the study staff will ask for a final update after one well-baby visit with the pediatrician.

Always report the diagnosis as the AE or SAE term. When a diagnosis is unavailable, report the primary sign or symptom as the AE or SAE term with additional details included in the narrative until the diagnosis becomes available. If the signs and symptoms are distinct and do not suggest a common diagnosis, report them as individual entries of AE or SAE.

Laboratory results, vital signs, and other diagnostic results or findings should be appraised by the Investigator to determine their clinical significance. Isolated abnormal laboratory results, vital sign findings, or other diagnostic findings (ie, not part of a reported diagnosis) should be reported as AEs if they are symptomatic, lead to study drug discontinuation, dose reduction, require corrective treatment, or constitute an AE in the investigator's clinical judgment.

For events that are serious due to hospitalization, the reason for hospitalization must be reported as the serious adverse event (SAE; diagnosis or symptom requiring hospitalization). A procedure

is not an AE or SAE, but the reason for the procedure may be an AE or SAE. Pre-planned (prior to signing the Informed Consent Form) procedures, treatments requiring hospitalization for pre-existing conditions that do not worsen in severity, and admission for palliative or social care should not be reported as SAEs (see Section 10.2 for Definitions).

For deaths, the underlying or immediate cause of death should always be reported as an SAE.

Any SAE that may occur subsequent to the reporting period (end of the on-treatment period) that the Investigator assesses as related to study drug should also be reported.

All AEs, SAEs, AESIs, and pregnancy reports are to be reported according to the procedures in Section 10.1.3.

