## 6. STUDY DESIGN

# 6.1. Study Description and Duration

This is a phase 3, randomized, double-blind, parallel-group, multi-dose study in approximately 630 cat-allergic adult and adolescent patients (ages  $\geq 12$  to <18 years), where permitted, with allergic rhinitis with or without conjunctivitis and with or without asthma.

- Cat allergic patients living with a cat who are significantly symptomatic while using standard of care anti-allergy medications will be enrolled in the study. The study includes a screening period of up to 12 weeks to ensure sensitization, symptom and medication use requirements are met during the baseline period.
- Randomization to 1 of 2 treatment arms (1:1)
  - o REGN1908-1909 600 mg (300 mg per mAb)
  - o Placebo that replaces REGN1908-1909
- Study drug will be administered Q12W for a total of 5 administrations
- End of treatment visit at week 60
- End of study safety follow-up visit at week 72

The screening period is set up to be a long enough duration so that the baseline assessment will occur outside of relevant pollen seasons for patients who are pollen allergic. Efficacy assessments will be done during the initial 12 weeks (weeks 0 to 12) after the first dose and during the last 12-week period (weeks 48 to 60) after last dose (dose 5) of REGN1908-1909 or placebo. For those individuals with seasonal allergies, efficacy assessments will be timed by the investigational site to ensure that the assessments are outside of any relevant pollen seasons. The study flow diagram is depicted in Figure 1. For prohibited medications and washout durations for different study procedures and assessment periods, see Section 8.9.1.

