Visit	Screening Visit 1 	Baseline V2 	R V3 	Tel V4	Tel V5	V6	Tel V7	V8	Tel V9	V10	Tel V11	V12	Tel V13	EOT V14	EOS V15	Un- scheduled Visit 
Day	-85 to	o -1	1	8	43	85	127	169	211	253	302	337	365	421	505	
Window (day)				±3	±7	±14	±7	±14	±7	±14	±7	±14	±7	±7	±7	
Week	- 1	2	0	1	6	12	18	24	30	36	43	48	52	60	72	
Efficacy:	-				L	 				.					.	
TNSS, TOSS, DMS		X	Nightly i	n e-dia	ary							N	ightly in			
PGIS			X			X								X		
PGIC						X										
RQLQ(S)			X			X						X		X		
Evaluation of cat exposure						X		X		X		Daily in e-diary				X
Patient Experience Assessment														X		
Spirometry 	$X^6$		$X^6$			$X^7$						$X^7$		$X^7$		
ACQ-5 for asthma patients 			$X^6$			X 						$X^7$		$X^7$		
ANSD and nighttime awakening for asthma patients 		$X^7$	Daily in	e-diar	y 							Daily in e-diary 				
ADSD and asthma rescue med use for asthma patients 		X 	Nightly i	n e-dia	ıry 							N	ightly in 6	e-diary 		
Safety:					1			- 0			ı	2				
Vital signs 	X	X	X 			$X^8$		$X^8$		$X^8$		X8		X	X	X
Physical examination	X		X			X		X		X		X		X	X	X
ECG	X											-				X
Adverse events	X ←														>	· X

	Screening	Period 	Randomization				Doubl	e-Blind	l Treat	tment l	Period			Follow Up		
				Initial Efficacy Assessment									nal nary) cacy sment	End of Treatment (EOT)/ Early Term.	End of Study (EOS)	
Visit	Screening Visit 1 	Baseline V2 	R V3 	Tel V4	Tel V5	V6	Tel V7	V8	Tel V9	V10	Tel V11	V12	Tel V13	EOT V14	EOS V15	Un- scheduled Visit 
Day	-85 to	o -1	1	8	43	85	127	169	211	253	302	337	365	421	505	
Window (day)				±3	±7	±14	±7	±14	±7	±14	±7	±14	±7	±7	±7	
Week	- 1	2	0	1	6	12	18	24	30	36	43	48	52	60	72	
Laboratory Testing:																
Hematology	X					X		X		X		X		X		X
Blood chemistry	X					X		X		X		X		X		X
Serum pregnancy test for WOCBP	X															X
Urine pregnancy for WOCBP 		X	X			X		X		X		X		X		X
FSH test for postmenopausal women only 	X															
Urinalysis	X															X
Serum for specific IgE for Fel d 1 and cat	X		X													
Serum for sIgE for Fel d 2, 4, and 7			X			X								X		
Serum for sIgE for other allergens (eg, HDM, etc)	X		X													
PK and ADA:																

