# 9.2. Study Procedures

All study procedures should be performed and/or collected at time points according to Table 3. For adolescent patients, parent(s)/caregiver(s) may assist in filling out questionnaires as needed.

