#### 11.4.6.1. Adverse Events

#### **Definitions**

For safety variables, 3 observation periods are defined:

- The pretreatment period is defined as the time from signing the ICF to before the first dose of study drug.
- The on-treatment period is defined as the day from first dose of study drug to the last dose of study drug plus 12 weeks (weeks 0 to 60).
- The follow-up period is defined as the end of the on-treatment period to 12 weeks after the end of the on-treatment period (weeks 60 to 72).

Treatment-emergent adverse events are defined as those that are not present at baseline or represent the exacerbation of a pre-existing condition during the on-treatment and follow-up periods.

Adverse events of special interest (Section 10.2.3 and Section 10.1.3) for this study include:

- Severe or systemic hypersensitivity reactions defined using the narrow SMQ for hypersensitivity, with manual adjudication of relevant PTs by medical monitor before database lock.
- Asthma exacerbations defined using the narrow SMQ for asthma and further manually adjudicated for events requiring treatment with systemic corticosteroids or resulting in an emergency room visit or hospitalization.

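### Protocol 10.1.1 stops routine adverse event recording at the end of the on-treatment period (week 60 after five doses), but the safety endpoint and the SAP need events to the end of study visit at week 72

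*Protocol*

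**What the plan says.** **Where recording stops.** Protocol 10.1.1 sets the recording window as "from the time of signing the ICF to the end of on-treatment period (see Section 11.4.6.1". The section it cites defines the on-treatment period as running from first dose to "last dose of study drug plus 12 weeks (weeks 0 to 60". Later in 10.1.1 the same point is named as the end of the reporting period, and what remains reportable is "Any SAE that may occur subsequent to the reporting period (end of the on-treatment period) that the Investigator assesses as related to study drug".

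**Where the rest of the plan runs.**
- Protocol 10.1.1 itself: "At each visit, the investigator will determine whether any AEs have occurred by evaluating the patient". The visits include the end of study visit.
- Protocol 6.1: "End of study safety follow-up visit at week 72".
- Protocol 4.2: the incidence of TEAEs, AESIs and serious TEAEs is a secondary endpoint for weeks 0 to 72.
- Protocol 11.4.6.1: TEAEs are counted in the on-treatment period and in the follow-up period, the latter being "end of the on-treatment period to 12 weeks after the end of the on-treatment period (weeks 60 to 72".
- SAP 4.6.1: AEs and SAEs are gathered from consent, visit by visit, through study end.
- SAP 5.7: the window for detecting events is first injection to EOS.
- SAP 5.7.1: TEAEs are summarised separately for the 60-week treatment period, for follow-up and for the whole study.

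Protocol Table 3 also has a row headed "Adverse events", and Protocol 9.2 says "All study procedures should be performed and/or collected at time points according to Table 3".

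**The concern.** The section that tells sites what to record ends earlier than the sections that say what will be analysed. The wording is not a passing slip, because 10.1.1 states the cutoff and then builds a narrower rule on it for later events. Under that rule a non-serious AE, a non-serious AESI or an SAE considered unrelated, with onset after week 60, need not be recorded. Each of these belongs to the weeks 0 to 72 endpoint.

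At stake is the meaning of the follow-up and whole-study TEAE tables. If some sites record to week 72 and others stop at week 60, a low follow-up count could reflect non-recording rather than few events, and the table would not show which. Events not asked about at the time are hard to recover later.

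A second, smaller problem concerns patients who stop study drug but stay in the study, as Protocol 8.3.2 and 9.1.2 encourage. Protocol 11.4.6.1 and SAP 4.6.1 define the periods in two ways at once: by time since last dose, and by fixed weeks (Protocol) or visits 3 to 14 and 14 to 15 (SAP). The two agree only for patients who receive all five doses.

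**Working it through.** This is date arithmetic on the nominal schedule.

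**Inputs.** Doses at weeks 0, 12, 24, 36 and 48, the last on day 337 (Protocol Table 3). On-treatment end = last dose + 12 weeks; follow-up end = 12 weeks after that (Protocol 11.4.6.1). End of treatment visit on day 421 and end of study visit on day 505 (Table 3).

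**The plan's own figures, five doses.**
- On-treatment end: 48 + 12 = week 60; 337 + 84 = day 421, the end of treatment visit.
- Follow-up end: 60 + 12 = week 72; 421 + 84 = day 505, the end of study visit.

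Both match the stated weeks and days.

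**Gap, five doses.** 505 − 421 = 84 days = 12 weeks; 12/72 = 16.7% of the time from first dose to end of study.

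**Patients who stop early but stay to week 72.** Under the last-dose anchor, recording stops at w + 12, where w is the week of the last dose. The last-dose follow-up period ends at w + 24, and the gap to week 72 is 72 − (w + 12). Under the fixed-week or visit anchor, recording stops at week 60 whatever w is, and the gap is 72 − 60 = 12 weeks.

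| Doses received | Last dose (week) | Last-dose anchor: recording stops | Last-dose anchor: follow-up ends | Last-dose anchor: gap to week 72 | Fixed anchor: gap to week 72 |
|---|---|---|---|---|---|
| 5 | 48 | 60 | 72 | 12 weeks | 12 weeks |
| 4 | 36 | 48 | 60 | 24 weeks | 12 weeks |
| 3 | 24 | 36 | 48 | 36 weeks | 12 weeks |
| 2 | 12 | 24 | 36 | 48 weeks | 12 weeks |
| 1 | 0 | 12 | 24 | 60 weeks | 12 weeks |

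The recording gap is therefore at least 12 weeks on either reading, and exceeds 12 weeks only on the last-dose reading.

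SAP 4.6.1 also describes an overall study period from first dose to the end of study visit and equates it with on-treatment plus follow-up. With the visit anchor that holds for everyone. With the last-dose anchor it fails for early stoppers by 72 − (w + 24) = 12, 24, 36 or 48 weeks after 4, 3, 2 or 1 doses.

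**The case against.** The strongest reply is that sites will record to week 72 anyway. Section 10.1.1 tells them to ask about AEs at each visit and to follow AEs to resolution or the last study visit. Week 72 is described as a safety follow-up visit. Section 10.1.3 lists SAEs and AESIs for reporting within 24 hours with no end date. This stands as far as likelihood goes: many sites would probably record throughout, so loss of events is a risk and not a certainty. It does not remove the conflict. The each-visit sentence sits in the same section as the cutoff, following a known AE to its outcome is not the same as recording a new one, and 10.1.3 governs speed. Read beside the related-SAE sentence, 10.1.3 leaves open whether unrelated SAEs and AESIs are still due.

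A second reply is that the gap for early stoppers is overstated. It stands. A reader might infer that these patients go unrecorded for 24 to 60 weeks, or that the SAP contradicts itself. The documents do not support either as fact, because the fixed-week and visit anchors give a consistent reading with a 12-week gap for everyone. The fair statement is that the definitions are ambiguous for these patients.

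Third, the Table 3 row is weak evidence. It is drawn as an arrow whose end cannot be read with certainty in the text version, and Protocol 9.2 says only that procedures should follow the table. Nothing here depends on that row.

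A reader might also infer a bias between arms. Patients and the site staff who assess them are blinded (Protocol 8.6), and nothing in the documents suggests that recording would differ by arm.

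**Conclusion.** The conflict is real. Protocol 10.1.1 is narrower than the endpoint, the TEAE definition and the SAP it should serve. For a five-dose patient the gap is 12 of 72 weeks (16.7%), from day 421 to day 505. For patients who stop drug early and stay, it is 12 weeks under the fixed anchor and 24, 36, 48 or 60 weeks under the last-dose anchor, and the plan does not say which applies.

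These figures assume nominal visit days and literal compliance with 10.1.1. They are weeks of observation, not missed events: the documents give neither the number of early stoppers nor an event rate. It would go too far to say that the weeks 0 to 72 endpoint cannot be estimated, since other instructions point sites to full recording.

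No efficacy result is affected. The AE hazard ratios cover the 60-week treatment period, so for five-dose patients the cutoff does not shorten them. The point should be corrected because it bears on a stated secondary endpoint and is cheap to repair.

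**What to change.** 1. In both places in Protocol 10.1.1, replace the end of the on-treatment period with the end of study visit (week 72, or the last study visit if earlier) for all AEs, SAEs and AESIs. Keep the related-SAE sentence for events after that visit.
2. In Protocol 11.4.6.1 and SAP 4.6.1, state one anchor for the on-treatment and follow-up periods of patients who stop drug early but remain in the study, so that together the periods run from first dose to the end of study visit, as SAP 4.6.1 already says.
3. If the last-dose anchor is kept for the on-treatment period, say in SAP 4.6.1 that follow-up would then last 24, 36, 48 or 60 weeks after 4, 3, 2 or 1 doses, against 12 weeks after five. The simple proportions in the follow-up table would not be comparable between such patients without that note.

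**Cost.** Wording in two protocol sections and one SAP section, plus a site notice. The protocol text needs an IRB/EC-approved amendment (Protocol 13.4 and 14) and can go with the next one. No visit or procedure is added: the week 72 visit exists, and patients who stop drug are already asked to attend the remaining visits.
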